11.4.2. Baseline Characteristics

Baseline and demographic characteristics will be summarized overall and by treatment group. For both continuous and categorical variables, appropriate summary statistics will be applied. For continuous variables, descriptive statistics will include the number of non-missing values, mean, standard deviation, median, minimum, and maximum. For categorical variables, descriptive statistics will include counts and percentages per category.

11.4.3. Safety Analysis Plan

Safety evaluations will be based on the incidence, severity, and type of clinically significant physical examination findings, clinically significant vital signs, and SAEs as defined in Section 9.2.2. Safety variables will be tabulated and presented for all subjects in the safety population, grouped by treatment group.

SAEs will be coded by the Medical Dictionary for Regulatory Activities (MedDRA) for preferred term and system organ class. The rate and exact 95% confidence intervals of related SAEs in aggregate, and by MedDRA categories, will be computed. The number of SAEs will be reported by a detailed listing showing the type, MedDRA coding, relevant dates (administration and adverse event), severity, relatedness, and outcome for each event.

Laboratory toxicities will be analyzed by taking the most severe response over the follow-up period, dichotomizing into a binary variable (none or mild versus moderate or severe) and using exact confidence intervals to summarize the event and toxicity rates. Tabular and graphical summaries of events will be presented for each solicited symptom, by type, severity (none, mild, moderate, severe), and time point post-administration.

Laboratory and vital sign data will also be presented as change from baseline. Variable transformations will be applied as appropriate. Shift tables may be produced for select laboratory parameters.

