2.3. Potential Risks and Benefits

2.3.1. Potential Risks

The potential risks of this study are those associated with having blood drawn, possible reactions to the fluconazole treatment and breach of confidentiality.

Most individuals who enroll in this study will not be infected with coccidioidomycosis and will not have a condition known as Valley Fever Pneumonia. Therefore, many of the individuals in the active treatment arm will be receiving an antifungal agent even though they have no fungal infection. Fluconazole will be dosed to treat coccidioidomycosis pneumonia based on existing Infectious Diseases Society of America (IDSA) recommendations for the treatment of non-meningeal infections in non-immunocompromised hosts. The treatment of coccidioidomycosis with fluconazole is not a listed indication on the package insert.

Fluconazole: Fluconazole has a well described safety profile and well defined adverse reactions that include: headaches (13%), nausea (7%), abdominal pain (6%), diarrhea (up to 3%). In less than 1% of individuals taking this medication there is a perversion of taste. Other less common side effects may include: serious liver damage, including death (signs include dark urine, light-colored stools, vomiting, or having severe skin itching), or an allergic reaction (signs include shortness of breath; coughing; wheezing; fever; chills; throbbing of the heart or ears; swelling of the eyelids, face, mouth, neck, or any other part of the body; or skin rash, hives, blisters or skin peeling). There are rare reports of exfoliative dermatitis, some of which were fatal. Individuals who have contraindications for treatment with fluconazole (e.g., allergy, intolerance, or contraindicated concomitant medications) will not be enrolled in the study. For patients who do not have coccidioidomycosis pneumonia but receive fluconazole, there is expected only a minimal increase in treatment-related risks.

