- The proportion of subjects who received at least one dose of the intervention and who exhibit an increase in liver function tests from baseline (pre-treatment Day 1) as defined as: confirmed AST elevation of >5X ULN or greater than or equal to 225 IU/L or ALT elevation of >5X ULN or greater than or equal to 250 IU/L or total bilirubin elevation >1.5X ULN or aminotransferase elevation of >3X ULN accompanied by total bilirubin elevation >1.5X ULN.

Exploratory Outcome 8:

- The adherence to long term self-administration of daily medications will be assessed in this order of precedence:
 - First: The mean number of pills taken as assessed by pill-count on Days 22, 29 and 43.
 - Second: Subject self-reported adherence as reported on Days 22, 29 and 43.

Exploratory Outcome 9:

- The proportion of subjects with a detectable fluconazole level as assessed by blood test on Days 22 and 43 in fluconazole recipients.
 - Plasma fluconazole concentration will be determined by high-performance liquid chromatography (HPLC)

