5.3.3. Reasons for Withdrawal and Discontinuation of Study Product Administration

Subjects may voluntarily withdraw their consent for study participation at any time and for any reason, without penalty. Subjects may also withdraw voluntarily from receiving the study intervention for any reason. An investigator may also withdraw a subject from receiving the study intervention for any reason. If a subject withdraws or is withdrawn prior to completion of the study, the reason for this decision must be recorded in the case report forms (CRFs). Follow-up safety evaluations will be conducted, if the subject agrees.

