9.2. Methods and Timing for Assessing, Recording, and Analyzing Safety Parameters

9.2.1. Adverse Events

Adverse Event (AE): International Conference on Harmonisation (ICH) E6 defines an AE as any untoward medical occurrence in a patient or clinical investigation subject administered a pharmaceutical product regardless of its causal relationship to the study treatment. FDA defines an AE as any untoward medical occurrence associated with the use of a drug in humans, whether or not considered drug related. An AE can therefore be any unfavorable and unintended sign (including an abnormal laboratory finding), symptom, or disease temporally associated with the use of a medicinal (investigational) product.

As the safety profile of fluconazole is well established, and this trial is not powered to detect new, unknown safety signals, **there will be no non-serious AE collection in this trial.**

Relationship to Study Products: The licensed study physician's assessment of a SAE's relationship to study product is part of the documentation process, but it is not a factor in determining what is or is not reported in this trial. If there is any doubt as to whether a clinical observation is an SAE, the event should be reported. The relationship to study product must be assessed for SAEs using the terms: related or not related. In a clinical trial, the study product must always be suspect. To help assess, the following guidelines are used:

-
- **Related** – There is a reasonable possibility that the study product caused the adverse event. Reasonable possibility means that there is evidence to suggest a causal relationship between the study product and the adverse event.
 - **Not Related** – There is not a reasonable possibility that the administration of the study product caused the event.

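### Section 11.4.3 prespecifies no fluconazole-versus-placebo estimate for laboratory toxicity or the liver outcome, so the excess liver risk has no planned interval

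*Combined protocol and SAP*

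**What the plan says.** Protocol section 11.4.3 sets out the safety analysis. On layout: "Safety variables will be tabulated and presented for all subjects in the safety population, grouped by treatment group". On serious events: "The rate and exact 95% confidence intervals of related SAEs in aggregate, and by MedDRA categories, will be computed". Laboratory toxicities are reduced to each subject's worst result over follow-up, by "dichotomizing into a binary variable (none or mild versus moderate or severe"), and then reported "using exact confidence intervals to summarize the event and toxicity rates". The section also plans change-from-baseline displays and possible shift tables. It specifies no risk difference, ratio, interval for a difference or test between arms.

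The liver outcome is Exploratory Outcome 7 in section 3.2.3: "The proportion of subjects who received at least one dose of the intervention and who exhibit an increase in liver function tests from baseline", followed by the laboratory limits. Neither a comparison nor a breakdown by arm is stated there.

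Other safety data are restricted by design. Section 9.2.1 says that "there will be no non-serious AE collection in this trial". Section 9.2.2 limits protocol SAEs to congenital anomalies or birth defects and to serious events that are both unexpected and suspected to be directly caused by study drug.

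For efficacy the plan does specify contrasts: a Z test of the difference in section 11.4.4.1, and a 95% interval for the difference in response proportions for secondary objective 6 in Table 11. Sections 11.4.4 and 11.4.4.3 leave efficacy and exploratory efficacy details to a separate statistical analysis plan. Section 11.4.3 makes no such deferral for safety.

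**The concern.** The trial tests empiric treatment. Section 11.2.1 assumes that 20% of enrolled subjects are cocci-positive, so about 0.8 × 500 = 400 of the 500 fluconazole recipients would take the drug without meeting the case definition. For patients without the disease, section 2.3.1 expects that "there is expected only a minimal increase in treatment-related risks". The placebo arm allows that increase to be estimated from randomized data, but the stated analysis does not call for the estimate.

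The gap matters most for the liver. Sections 2.3.1 and 9.1 already describe liver toxicity as a reaction to fluconazole. Many liver events would therefore count as expected and fall outside the protocol's SAE definition. With non-serious events uncollected, the laboratory summaries carry most of the liver evidence. If they appear only as rates with an exact interval around each, the natural reading is to check whether the intervals overlap. That is an inefficient guide to whether the arms differ.

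**Working it through.** **The plan's own figures.** The documents give no expected liver-event rate, precision or power for safety, so there is no safety figure to reproduce. As a check on the arithmetic, the primary power in section 11.2.1 (0.20 vs 0.40, 100 per arm, two-sided 0.05) does reproduce. With unpooled variance it is Φ(0.20/√(0.2×0.8/100 + 0.4×0.6/100) − 1.96) = Φ(3.162 − 1.960) = 88.5%. With pooled null variance it is 87.6%, the Table 5 entry. The plan states 88%.

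**Inputs.** 500 per arm (Table 1; 1:1 allocation in section 5.3.1), taking all randomized subjects as dosed. 95% exact intervals: section 11.4.3 gives the 95% level for SAEs, and it is assumed here for laboratory toxicities too. The intervals are taken as one per arm, which is inferred from the by-group presentation. Liver-event rates of 1% to 10% are assumptions.

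**Formulas.**
- Exact (Clopper-Pearson) interval for x events in n: lower limit = Beta quantile 0.025 (x, n−x+1); upper limit = Beta quantile 0.975 (x+1, n−x).
- Newcombe interval for d = p₁ − p₂, with Wilson limits (l₁, u₁) and (l₂, u₂): lower = d − √[(p₁−l₁)² + (u₂−p₂)²]; upper = d + √[(u₁−p₁)² + (p₂−l₂)²].

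**One data set: 15/500 on fluconazole, 5/500 on placebo.**
- Exact intervals: 1.7% to 4.9% and 0.3% to 2.3%. They overlap.
- Wilson limits: 0.01826 to 0.04890 and 0.00428 to 0.02319.
- Lower limit for the difference: 0.02 − √[(0.03−0.01826)² + (0.02319−0.01)²] = 0.02 − 0.0177 = 0.0023.
- Upper limit: 0.02 + √[(0.04890−0.03)² + (0.01−0.00428)²] = 0.02 + 0.0198 = 0.0398.
- The difference is 2.0 points, 95% interval 0.2 to 4.0, which excludes zero.

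**How wide the zone of disagreement is.** With 10 placebo events, the difference interval lies above zero from 21 fluconazole events, while the exact intervals do not separate until 28. Every count from 21 to 27 gives overlapping intervals and a difference interval above zero.

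**How often this happens.** Summing binomial probabilities over all pairs of counts, 500 per arm:

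| True rate, placebo vs fluconazole (assumed) | Exact intervals separate | Difference interval above 0 |
|---|---|---|
| 1% vs 1% (no excess) | 0.1% | 1.9% |
| 1% vs 2% | 3.5% | 22.0% |
| 1% vs 3% | 22.9% | 60.3% |
| 2% vs 5% | 37.6% | 74.3% |
| 3% vs 7% | 51.6% | 83.8% |
| 5% vs 10% | 55.4% | 85.8% |

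From 1% vs 3% downwards, judging by overlap loses about 30 to 37 percentage points; at 1% vs 2% the loss is 18.5.

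**Whether the halting rule closes the gap.** Section 9.5 counts liver elevations among all randomized subjects, arms together, against more than 10%. Rates of 2% and 5% pool to (2+5)/2 = 3.5%, and 2% and 15% pool to 8.5%. The rule is not a between-arm comparison and does not supply one.

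**The case against.** The strongest reply is that the plan contains no overlap rule. Section 11.4.3 uses intervals to summarize rates, and no safety decision depends on whether they separate. A table showing 5/500 and 15/500 already shows a 2-point difference, and anyone can compute its interval from those counts. A reader might infer that a real liver excess would go unrecognised. The documents do not support that: rates will stand side by side, section 9.6.2 allows the DSMB data by group and unblinded liver rates, and a final unblinded review of cumulative safety data is planned. The table above shows the cost only if a reader judges by overlap.

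A reader might also infer that no liver contrast is planned anywhere. The separate analysis plan is not supplied. Its stated scope is efficacy, but it may cover Exploratory Outcome 7.

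A third tempting step is to ask for discontinuation of study drug by reason, as data already held. The sentence in section 5.3.3 that "the reason for this decision must be recorded in the case report forms (CRFs") applies to subjects who withdraw or are withdrawn before completing the study. Section 5.3.3.1 keeps subjects taken off drug in follow-up. The text does not clearly show that their reasons for stopping are recorded, so that request is not made here.

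Descriptive safety is also a deliberate choice: section 9.2.1 says the trial is not powered for new, unknown signals, and the liver objective is to characterize. That stands as a reason not to test. It is not a reason to omit an estimate, because liver toxicity is a known reaction and a difference with an interval needs no power claim.

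**Conclusion.** The point holds as a minor analysis improvement. The supplied text prespecifies no fluconazole-minus-placebo estimate or interval for laboratory toxicity or for Exploratory Outcome 7, although laboratory data are the main liver evidence. The consequence is that the excess is left unquantified in the plan and a moderate one could be misread, not that it would be hidden. At assumed true rates of 1% and 3% with 500 per arm, the separate exact intervals part in 23% of trials and the difference interval lies above zero in 60%. These figures rest on assumed event rates, on one interval per arm, and on a reader who compares the intervals. If the intervals were meant to be pooled over arms, even less would be said about the difference.

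**What to change.** In section 11.4.3, for the Exploratory Outcome 7 composite and for each dichotomized laboratory toxicity, add the difference in proportions (fluconazole minus placebo) in the safety population with a 95% interval by the Newcombe or Miettinen-Nurminen method. State that these are descriptive estimates without multiplicity adjustment. Keep the exact intervals, and say explicitly that they are computed by arm. If the separate analysis plan already specifies such a contrast for the liver outcome, refer to it in 11.4.3 and extend it to the laboratory toxicities.

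The cost is a few extra table columns; no new data, visits or subjects are needed. The drawback is several unadjusted intervals. With equal true rates of 1%, each would lie wholly above zero about 2% of the time, and that chance accumulates over the parameters reported, which is why the descriptive label matters.

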11.4.4. Efficacy Analysis Plan

A separate statistical analysis plan document will be generated which will contain the details of the efficacy analyses. In this section below, the primary efficacy analysis is described and the secondary efficacy analyses are briefly outlined. The exploratory efficacy analyses will be addressed in the statistical analysis plan and are not described here.

11.4.4.1. Primary Efficacy Analysis

The primary efficacy analysis tests the difference between the fluconazole and placebo treatment groups in the proportion of subjects with an occurrence of clinical response at Day 22. Subjects without a clinical response at Day 22 will be coded as treatment failures while subjects with a clinical response at Day 22 will be coded as an observed event if the clinical response outcome measure definition (Section 3.2.1) is met.

A test of difference between the proportion of clinical responses in the fluconazole and placebo groups at the Day 22 time point will be performed using the Z test. The use of this test statistic will permit us to use the method of B-values to calculate conditional power of the test in the planned futility analyses, as outlined in “Statistical Monitoring of Clinical Trials, a Unified Approach”, by Proschan et al [22]. Details of this procedure will be provided in the statistical analysis plan.

The primary efficacy analysis will be performed in the cocci-positive per protocol analysis population. Secondary analyses will be performed in the all randomized per protocol population, all randomized and cocci-positive ITT and the mITT populations (see also Secondary Objectives 1 and 6). Sensitivity analyses, which will assess the impact of drop-out, censoring mechanisms, and analysis methods on the primary analysis, may be performed. These analyses will be specified in the separate statistical analysis plan document.

In addition to the planned tests of hypotheses, descriptive analyses will be performed for the primary endpoint. The number of clinical responses observed will be tabulated by time point, including and beyond Day 22, and treatment group. Tabular and graphical summaries will be prepared for the composite MSG score across all assessment time points.

To investigate whether there is evidence of a differential diagnosis of coccidioidomycosis between treatment arms, which might result in selection bias for inclusion in our primary analysis, the number of coccidioidomycosis cases in each treatment arm will be compared among all randomized subjects.

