5.3. Treatment Assignment Procedures

5.3.1. Randomization Procedures

Per International Conference on Harmonisation (ICH) guideline E6: Good Clinical Practice (GCP), screening records will be kept at each participating site to document the reason why an individual was screened, but failed trial entry criteria. The reasons why individuals failed

screening will be recorded in the Statistical and Data Coordinating Center's (SDCC) AdvantageEDCSM (Electronic Data Capture System).

Using a centralized randomization system, eligible subjects will be randomly assigned to 1 of 2 groups (1:1 ratio) to receive either 42 days of placebo or 400 mg/day fluconazole capsules. The randomization code will be prepared by statisticians at the SDCC and sent to the DMID Clinical Agents Repository where the study product will be labeled with a randomization code which links to the treatment assignment. Once consented and determined to be eligible for the trial, the subject will be assigned the next available assignment in sequence of the product available at the site. The randomization code of the distributed study product will be entered into AdvantageEDC upon enrolling the subject in the trial. Instructions for use of the enrollment module are included in the AdvantageEDC User's Guide.

If emergency unblinding is required, the site may determine the treatment assignment by contacting the SDCC or through AdvantageEDC.

Subjects who sign the informed consent form and are randomized but do not ingest the study drug will be replaced. Subjects who sign the informed consent form, and are randomized, receive the study drug, and subsequently withdraw consent, are withdrawn or terminated from the study, or are lost to follow-up will not be replaced.

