At the screening visit a physical examination will be performed by a clinician licensed to make medical diagnoses. A standard of care physical exam completed by a clinical provider within the 72 hours prior to screening may be used for the screening exam if all appropriate organ systems are examined and documented. The comprehensive physical examination must include the following organ or body system assessments: skin; head, eyes, ears, nose, and throat; thyroid; neurological; chest and lungs; cardiovascular; abdomen (liver and spleen); lymph nodes; musculoskeletal, genitourinary and extremities. Assessments of any specific signs or symptoms reported by the subject must also be performed and documented. Findings from the screening must be characterized as either normal or abnormal, and if abnormal, a description of the abnormality must be provided. Following the screening visit physical examination, targeted physical exams will be performed on Days 22, 29, and 43 if indicated based the subject's interim

medical history, and changes must be classified as new, worsened, or improved from those at screening.

Vital signs (sitting heart rate, sitting blood pressure (mmHg), respiratory rate, oral temperature (°C), oxygen saturation (SpO₂)) and weight will be collected at the screening visit, Days 22, 29, and 43. Vital signs assessed on Day 1 will be considered as baseline. Subjects must not eat anything hot or cold or smoke within 10 minutes prior to taking oral temperature. Height will be collected on Day 1.

A resting 12-lead ECG will be performed at Day 1 or the pre-screening visit and at early termination visits when applicable. An ECG completed as part of standard of care within the past 72 hours and that is available to the study team at the time of screening can serve as the screening ECG and does not require repeating. The ECG will be assessed for QT prolongation as well as other abnormalities indicative of QT prolongation while the subject is on-site for their study-related visit by a clinician licensed to make medical diagnoses.

The FLEET CAP score is an efficacy outcome measure based on a clinical scoring system that allows a constellation of clinical symptoms to be quantified and scored over time: cough, fatigue, chest pain, dyspnea, sputum production, night sweats, fever, and hypoxia. The FLEET CAP score will be completed on Days 1, 22, 29, and 43.

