11.2. Sample Size Considerations

11.2.1. Sample Size for Per Protocol Analysis Population

The primary analysis will compare the proportion of subjects achieving clinical response at Day 22 among efficacy evaluable subjects, defined as subjects in the Cocci-Positive Per Protocol analysis population who meet the case definition of coccidioidomycosis pneumonia who were compliant with the intervention administration and have coccidioidal serology data available at the Day 1 and 22 visits. We further assume that the clinical response proportion at Day 22 will be 0.20 in the placebo arm, and 0.40 in the fluconazole arm. As described in section 11.2.3, enrollment will continue until 200 subjects are evaluable for efficacy, 100 in each treatment arm, which suffices for 88% power for the Z test with unpooled variance to compare proportion of clinical responses at Day 22 at the two-sided level of 0.05. This is the primary sample size calculation which forms the basis for target enrollment to the study and for subsequent sample size re-estimation procedures at scheduled interim analyses while the study is enrolling.

A secondary analysis in the Cocci Positive Modified Intent-to-Treat population will compare the proportion of responders at Day 22, treating subjects dropping out before the Day 22 visit as non-responders. Assuming that the probability of drop-out before Day 22 is 20% among cocci-positive subjects, we would expect that 250 cocci-positive subjects would be available for this secondary analysis as a result of reaching the target sample size of 200 cocci-positive subjects with Day 22 follow-up for the primary analysis. Since subjects who drop-out are considered non-responders, the probability of response in the control-arm subjects would be $0.8 * 0.2 = 0.16$, and in the treated subjects would be $0.8 * 0.4 = 0.32$. The Z-test with unpooled variance has power of 85% to detect this difference in response proportions with 125 cocci-positive subjects per arm.

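### The primary Day 22 test uses no covariate although every subject has a Day 1 FLEET CAP score; adjusting for it is a cheap improvement whose power gain is unknown and probably small.

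*Combined protocol and SAP*

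**What the plan says.** Section 11.4.4.1 states that the difference between arms "at the Day 22 time point will be performed using the Z test". It names no covariate and gives one reason for the choice: "The use of this test statistic will permit us to use the method of B-values to calculate conditional power of the test". The primary population is the cocci-positive per-protocol population.

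The design figures are in Section 11.2.1. The planning assumption is that "the clinical response proportion at Day 22 will be 0.20 in the placebo arm, and 0.40 in the fluconazole arm". The target is 200 evaluable subjects, split equally between the arms, a number "which suffices for 88% power for the Z test with unpooled variance". The test is two-sided at 0.05.

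On the baseline measure, Section 8.1 says: "The FLEET CAP score will be completed on Days 1, 22, 29, and 43". Section 3.2.1 defines response as a fall of half or more from the subject's own Day 1 score. Section 5.3.1 describes 1:1 randomisation and mentions no stratification by that score.

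Section 11.4.4.1 allows optional sensitivity analyses on drop-out, censoring and analysis methods, without naming baseline adjustment. Section 11.4.4 leaves the details to a separate SAP, which is not part of the supplied text.

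**The concern.** A baseline measure related to the outcome, collected on everyone and left out of the primary model, is a usual place to look for unused precision. Two features of this trial make it worth asking.

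First, baseline could plausibly predict response. The score is a sum of integer items from 0 to 22, and eligibility sets no minimum. A subject who starts at 1 must reach 0 to respond; one who starts at 3 must reach 1 or less, a fall of two thirds. Measurement error in a high Day 1 score works the other way and makes a later halving easier.

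Second, the primary population is about 20% of those enrolled (Section 11.2.3). It is selected after randomisation, by serology through Day 29 and by at least 80% adherence (Sections 3.2.1 and 11.4.1). Randomisation therefore does not guarantee balance in severity within it. Section 11.4.4.1 itself raises the possibility of selection bias from differential diagnosis.

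At stake are some precision in the primary estimate and protection against a visible severity imbalance that would otherwise complicate its interpretation.

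**Working it through.** **Inputs from the documents.** Response 0.20 (placebo) and 0.40 (fluconazole); 100 per arm; two-sided 0.05; stated power 88% (Section 11.2.1), with 87.6% in Table 5 (Section 11.2.2).

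**Step 1: reproduce the stated power.**
- Unpooled: SE = sqrt((0.20×0.80 + 0.40×0.60)/100) = sqrt(0.40/100) = 0.0632. Power = Φ(0.20/0.0632 − 1.96) = Φ(1.202) = 88.5%.
- Pooled: the mean proportion is 0.30, so power = Φ((0.20×10 − 1.96×sqrt(2×0.30×0.70))/sqrt(0.40)) = Φ(1.154) = 87.6%, the Table 5 entry.

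The text and the table appear to use different variance forms. The difference is under 1 point, and the 88% stands.

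**Step 2: formula power after adjustment.** Let R² be the share of within-arm variance in response explained by the Day 1 score. The adjusted standard error is approximately SE × sqrt(1 − R²), so power = Φ(0.20/(0.0632 × sqrt(1 − R²)) − 1.96). The equivalent unadjusted size is 100/(1 − R²) per arm. The documents give no R²; every value below is an assumption.

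| Assumed R² | Power, 0.20 vs 0.40 | Equivalent n per arm |
|---|---|---|
| 0% | 88.5% | 100 |
| 2% | 89.2% | 102 |
| 5% | 90.1% | 105 |
| 10% | 91.5% | 111 |

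For the attenuated effect that Section 11.2.2 discusses (0.20 versus 0.30), unpooled power is 37.6% at R² = 0 and 41.0% at R² = 10%.

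**Step 3: simulation.** 4,000 trials per setting, 100 per arm, one normally distributed baseline covariate with a logistic effect on response. The unpooled Z test was compared with a risk difference standardised from a logistic model (treatment plus baseline) with an influence-function standard error.

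| Log-odds per SD of baseline | Within-arm R² (placebo, fluconazole) | Unadjusted power | Adjusted power |
|---|---|---|---|
| 0 | 0%, 0% | 88.4% | 88.0% |
| 0.25 | 1.0%, 1.5% | 89.1% | 89.4% |
| 0.50 | 3.8%, 5.4% | 88.7% | 89.5% |
| 0.75 | 8.1%, 10.8% | 89.6% | 92.1% |

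The Monte Carlo standard error of each power figure is about sqrt(0.88×0.12/4000) = 0.5 points. At R² of about 5% the gain is 0.8 points, less than the formula suggests (90.1 − 88.5 = 1.6). With both rates at 0.20, rejection over these settings was 5.1% to 5.6% unadjusted and 5.1% to 5.5% adjusted, so the two tests behave alike.

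**Step 4: what R² might be.** Separate checks with proportional recovery on an integer score (all inputs assumed) put within-arm R² at about 0% to 3%. At 3%, power = Φ(3.162/sqrt(0.97) − 1.96) = Φ(1.251) = 89.4%, about 1 point above 88.5%.

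**Step 5: is the stated reason an obstacle?** B-values need an approximately normal Z statistic with approximately independent increments. A standardised risk difference divided by its robust standard error is approximately normal and can usually be monitored in the same way, but independent increments are not automatic if the logistic model is wrong. The stated reason does not rule out adjustment; it does call for a check.

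**The case against.** The strongest case for leaving the plan alone has four parts.

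1. The endpoint is already indexed to each subject's own baseline. A start of 4 needs a 2-point fall and a start of 16 needs 8, so if recovery is proportional to severity, baseline carries little further information. This stands, and it is why the gain may be near zero.
2. There is no shortfall to repair on the design assumptions. The 88% reproduces, enrolment is to continue until 200 are evaluable, and Section 11.3.3 raises the target if fewer are predicted. This stands. A reader might infer from the unadjusted test that power is being given away or that the trial is underpowered. The documents do not support either reading: they give no prognostic strength for the baseline score.
3. Tables 5 and 7-10 describe the plain Z test, so a new primary test means re-running the futility and re-estimation simulations. This stands as a cost.
4. A separate SAP may already contain an adjusted analysis. This cannot be excluded, but the supplied text names none and makes method-related sensitivity analyses optional.

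A reader might also infer that adjustment repairs the post-randomisation selection. It does not: it handles imbalance in measured baseline severity only. Comparing case counts by arm, which Section 11.4.4.1 plans, addresses a different part of that problem.

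None of this shows that adjustment would do harm. With a non-prognostic baseline, simulated power was 88.0% against 88.4%, a difference within Monte Carlo error.

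**Conclusion.** The point holds as an efficiency and robustness improvement of modest priority. The primary analysis makes no use, as a covariate, of a baseline score held on every subject, and the reason given for the plain Z test does not require that.

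The likely benefit in power is small: about 1 point or less if R² is 0% to 3%, under 1 point in simulation at about 5%, and around 3 points by formula at 10%, a level that nothing in the documents supports. These figures rest on an assumed R², on the planned 0.20 and 0.40, and on 100 evaluable subjects per arm. Adjustment would do little for the attenuated-effect scenario.

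The firmer argument is that a standardised estimate guards against imbalance in measured severity within a subset that randomisation does not protect.

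**What to change.** In Section 11.4.4.1, before any unblinded efficacy data are seen (the first futility look is at 500 enrolled), make the primary estimate the risk difference standardised from a logistic model with treatment and continuous Day 1 FLEET CAP score. Give it a robust standard error and test it with the resulting Z statistic. This still compares overall response proportions between arms, so the hypotheses in Section 11.1 need not change. Keep the unadjusted Z test as a named supportive analysis.

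Use the adjusted Z for the B-value conditional power only after simulation confirms that type I error and the operating characteristics in Tables 7-10 hold, with the baseline score simulated both as non-prognostic and as moderately prognostic.

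The cost is modest extra programming, a re-run of the existing simulations, and a short text change. No new data are needed.
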